3.5. Discontinuations

If the subject meets the Virologic Response-Based Stopping Criteria (Section 3.3.1), they should complete an Early Termination Visit as soon as possible after SOF/VEL is discontinued and complete post-treatment visits up to 30 days after the last dose of SOF/VEL and/or 60 days after the last dose of RBV to assess for safety.

If the subject meets the Stopping Rules for Individual Subjects (Section 3.4) or other criteria for discontinuation of study treatment (Section 3.7), prior to completion of SOF/VEL dosing period, the subject should complete an Early Termination Visit as soon as possible after SOF/VEL is discontinued and complete the post-treatment assessments as described in Section 6.3 and in Study Procedures [Appendix 2](#).

Subjects discontinuing treatment prior to completion of dosing period for reasons other than those described in Sections 3.3, 3.4 and 3.7 should complete an Early Termination Visit as soon

as possible after SOF/VEL is discontinued. The subject should also complete the post-treatment assessments as described in Section 6.3 and in Study Procedures Appendix 2.

3.6. Assessments for Premature Discontinuation from Study

If a subject discontinues SOF/VEL dosing (for example, as a result of an adverse event [AE]), every attempt should be made to keep the subject in the study and continue to perform the required study-related post-treatment assessments and procedures (see Section 6.3). If this is not possible or acceptable to the subject or investigator, the subject may be withdrawn from the study.

3.7. Criteria for Discontinuation of Study Treatment

When medically feasible, the Medical Monitor must be consulted prior to subject discontinuation.

Study drug must be discontinued in the following instances:

- Intercurrent illness that would, in the judgment of the investigator, affect assessments of clinical status to a significant degree
- Unacceptable toxicity, as defined in the toxicity management section of the protocol, or toxicity that, in the judgment of the investigator, compromises the ability to continue study-specific procedures or is considered to not be in the subject's best interest
- Subject requests to discontinue for any reason; it is important to determine whether the withdrawal of consent is primarily due to an AE, lack of efficacy, or other reason
- Subject non-compliance
- Pregnancy of female subject. Subjects randomized to Group 2 who have female partners who become pregnant must immediately contact the Principal Investigator in order to discuss the risks and benefits of continuing treatment with RBV. It is permissible to stop RBV but continue SOF/VEL in subjects that have pregnant female partners.
- Discontinuation of the study at the request of Gilead, regulatory agency or an IRB/IEC

3.8. Biomarker Testing

3.8.1. Biomarker Samples for Optional Future Research

PPD

PPD

3.8.2. Biomarker Samples for Optional Pharmacogenomic Research

PPD

4. SUBJECT POPULATION

4.1. Number of Subjects and Subject Selection

Approximately 200 chronic HCV Genotype 3 infected subjects will be randomized 1:1 into 2 treatment groups in this study. Patients will be stratified by treatment experience (treatment naïve versus treatment experienced).

In order to manage the total study enrollment, Gilead Sciences, Inc., at its discretion, may suspend screening and/or enrollment at any site or study-wide at any time.

4.2. Inclusion Criteria

Subjects must meet all of the following inclusion criteria to be eligible for participation in this study.

1. Willing and able to provide written informed consent
2. Male or female age ≥ 18 years
3. Chronic HCV infection (≥ 6 months) as documented by prior medical history or liver biopsy
4. Genotype 3 HCV at Screening as determined by the central laboratory. Any non-definitive HCV genotype results will exclude the subject from participation.
5. HCV RNA $\geq 10^4$ IU/mL at Screening
6. Confirmation of cirrhosis by any of the following methods:
 - a. Liver biopsy showing cirrhosis (eg., Metavir score=4 or Ishak score ≥ 5)
 - b. Fibroscan results > 12.5 kPa
 - c. Fibrotest result > 0.75 AND an AST platelet ratio index (APRI) > 2 during Screening
 - d. Liver imaging within 6 months of Baseline/Day 1 to exclude hepatocellular carcinoma (HCC)
7. Subjects must have a determination of treatment experience (treatment naïve v. treatment experienced). Treatment naïve is defined as having never been exposed to an approved or experimental HCV-specific direct acting antiviral agents or prior treatment of HCV with interferon or ribavirin. All other patients will be considered treatment experienced.
8. If treatment experienced, the subject's medical records must include details of prior treatment regimen(s). Any prior use of SOF or other nucleotide analogue HCV NS5B inhibitors should be documented. Previous use of an NS5A inhibitor is not allowed.

9. A negative serum pregnancy test is required for female subjects (unless permanently sterile or greater than two years post-menopausal).
10. Male subjects and female subjects of childbearing potential who engage in heterosexual intercourse must agree to use protocol specified method(s) of contraception as described in [Appendix 5](#).
11. Lactating females must agree to discontinue nursing before the first dose of study drug is administered.
12. Subject must be able to comply with the dosing instructions for study drug administration and be able to complete the study schedule of assessments.

Subjects with **HIV coinfection** may be eligible, provided they satisfy these additional inclusion criteria:

13. Completed at least 3 months of any prior HIV ARV therapy and maintained HIV RNA <50 copies/mL (or <LLOQ if the local laboratory assay's LLOQ is 50) copies/mL) and CD4 T-cell count > 100 cells/mm³ prior to Screening. Subjects with an isolated or unconfirmed HIV RNA >50 copies/mL (or >LLOQ if the local laboratory assay's LLOQ is 50) copies/mL) are not excluded

14. No history of HIV-associated opportunistic infections within 6 months of Screening. (see [Appendix 6](#))

15. On a stable, protocol-approved, ARV regimen for ≥ 8 weeks prior to Screening and is expected to continue the current ARV regimen through the end of study. HIV ARV agents allowed in this study are the following and should be administered per the prescribing information in the package insert:

— cobicistat/elvitegravir/emtricitabine/tenofovir disoproxil fumarate (Stribild)

OR

— emtricitabine/tenofovir disoproxil fumarate, emtricitabine/tenofovir alafenamide, or abacavir/lamivudine plus:

- ritonavir boosted atazanvir; or
- ritonavir boosted darunavir; or
- ritonavir boosted lopinavir; or
- raltegravir; or
- rilpivirine

OR

- cobicistat/elvitegravir/emtricitabine/tenofovir alafenamide (Genvoya[®])
 - a) Single tablet regimens containing emtricitabine/tenofovir disoproxil fumarate (Truvada[®]) plus rilpivirine (Eviplera[®]) or emtricitabine/tenofovir alafenamide plus rilpivirine) respectively are permitted.
 - b) Alternative combinations of the above listed medications may be allowed after discussion and approval by the Gilead Medical Monitor. Subjects taking ARV regimens not on the above list are excluded from this study.

4.3. Exclusion Criteria

Subjects who meet *any* of the following exclusion criteria are not to be enrolled in this study.

1. Current or prior history of any of the following:
 - a. Clinically-significant illness (other than HCV or HIV) or any other major medical disorder that may interfere with subject treatment, assessment or compliance with the protocol; subjects currently under evaluation for a potentially clinically-significant illness (other than HCV/HIV) are also excluded.
 - b. Gastrointestinal disorder or postoperative condition that could interfere with the absorption of the study drug.
 - c. Difficulty with blood collection and/or poor venous access for the purposes of phlebotomy.
 - d. Solid organ or bone marrow transplantation.
 - e. Significant pulmonary disease, significant cardiac disease, or porphyria.
 - f. Clinically significant hemoglobinopathy (e.g., sickle cell disease, thalassemia).
 - g. Psychiatric hospitalization, suicide attempt, and/or a period of disability as a result of their psychiatric illness within the last 5 years. Subjects with psychiatric illness (without the prior mentioned conditions) that is well-controlled on a stable treatment regimen for at least 12 months prior to enrollment or has not required medication in the last 12 months may be included.
 - h. Malignancy within the 5 years prior to screening, with the exception of specific cancers that have been cured by surgical resection (basal cell skin cancer, etc). Subjects under evaluation for possible malignancy are not eligible.

- i. Active, serious infection (other than HIV or HCV) requiring parental antibiotics, antivirals or antifungals within 30 days prior to baseline.
2. Child-Pugh-Turcotte (CPT) Score >7 at Screening
3. Current, uncontrolled ascites, variceal hemorrhage, hepatic encephalopathy, hepatorenal syndrome, hepatopulmonary syndrome, or other signs of decompensated cirrhosis
4. Screening ECG with clinically significant abnormalities
5. Subjects with the following laboratory parameters at screening:
 - HIV-1 RNA >50 copies/mL
 - CD4 T-cell count <100 cells/mm³
 - ALT > 10 × the upper limit of normal (ULN)
 - AST > 10 × ULN
 - Direct bilirubin > 1.5 × ULN
 - For subjects receiving ritonavir boosted atazanavir regimen, a direct bilirubin > 1.5 x ULN will be allowed if < 25% of the total bilirubin
 - Platelets < 50,000/μL
 - HbA1c > 8.5%
 - Creatinine clearance (CLcr) < 60 mL /min as calculated by the Cockcroft-Gault equation {Cockcroft et al 1976}
 - Hemoglobin < 10 g/dL
 - Albumin < 3 g/dL
 - INR > 1.5 x ULN unless subject has known hemophilia or is stable on an anticoagulant regimen affecting INR
 - HIV-2 positive test
 - Presence of HBV surface antigen
6. Prior exposure to VEL or any HCV NS5A inhibitor.
7. Pregnant or nursing female or male with pregnant female partner.

8. Females who may wish to become pregnant and/or plan to undergo egg harvesting during the course of the study and up to 6 months of the last dose of study drug
9. Chronic liver disease of a non-HCV etiology (e.g., hemochromatosis, Wilson's disease, alfa-1 antitrypsin deficiency, cholangitis).
10. Active infection with hepatitis B virus (HBV).
11. Infection with HIV 2
12. Clinically-relevant alcohol or drug abuse within 12 months of screening, as determined by the investigator. A positive drug screen will exclude subjects unless it can be explained by a prescribed medication; the diagnosis and prescription must be approved by the investigator.
13. Use of any prohibited concomitant medications as described in Section 5.5
14. Chronic use of systemically administered immunosuppressive agents (e.g., prednisone equivalent > 10 mg/day).
15. Known hypersensitivity to VEL, SOF (and metabolites), or RBV.
16. The presence of contraindications to RBV.
17. Participation in a clinical study with an investigational drug or biologic within 3 months prior to Baseline/Day 1.
18. Treatment for HCV infection with experimental or approved regimens within 3 months of Baseline/Day 1.

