1.2.2. Additional Clinical Experience

1.2.2.1. Sofosbuvir/Velpatasvir Phase 3 Studies

Four Phase 3 studies have been completed evaluating the efficacy and safety of SOF/VEL in subjects with genotype 1-6 HCV infection. Three studies enrolled subjects without cirrhosis or with compensated cirrhosis, GS-US-342-1138 (ASTRAL-1), GS-US-342-1139 (ASTRAL-2) and GS-US-342-1140 (ASTRAL-3); and one study enrolled subjects with decompensated cirrhosis GS-US-342-1137 (ASTRAL-4). Three Phase 3 trials enrolling patients with HIV-1 coinfection (GS-US-342-1202 [ASTRAL-5]), patients who failed to achieve SVR12 in previous Gilead sponsored HCV treatment studies (GS-US-342-1553), and patients who received placebo during ASTRAL-1 (GS-US-342-1446) are currently ongoing. Summaries of results from the completed Phase 3 studies and descriptions of the ongoing Phase 3 studies are presented below.

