1.2.2.1.4. Study GS-US-342-1137 (ASTRAL-4)

Study Design

This ongoing, Phase 3, randomized, open-label, multicenter study is assessing the antiviral efficacy, safety, and tolerability of SOF/VEL ±RBV for 12 weeks and SOF/VEL for 24 weeks in subjects with chronic HCV infection and Child-Pugh-Turcotte (CPT) class B cirrhosis. The study was conducted in the US.

Subjects with genotype 1 to 6 HCV infection with CPT class B cirrhosis were randomized (1:1:1) to SOF/VEL for 12 weeks (SOF/VEL 12 Week group), SOF/VEL +RBV for 12 weeks (SOF/VEL +RBV 12 Week group), or SOF/VEL for 24 weeks (SOF/VEL 24 Week group). Randomization was stratified by HCV genotype (1, 2, 3, 4, 5, 6, and indeterminate).

Disposition

A total of 267 subjects were included in the Safety and Full Analysis Sets (90 subjects in the SOF/VEL 12 Week group, 87 subjects in the SOF/VEL +RBV 12 Week group, and 90 subjects in the SOF/VEL 24 Week group).

Of the 90 subjects in the SOF/VEL 12 Week group, 89 subjects (98.9%) completed study drug and 1 subject (1.1%) discontinued due to an AE.

Of the 87 subjects in the SOF/VEL +RBV 12 Week group, 82 subjects (94.3%) completed study drug; 4 subjects (4.6%) discontinued due to AEs and 1 subject (1.1%) discontinued due to virologic failure (pharmacokinetic [PK] data for this subject indicated noncompliance with study drugs).

Of the 90 subjects in the SOF/VEL 24 Week group, 84 subjects (93.3%) completed study drug; 4 subjects (4.4%) discontinued due to AEs, 1 subject (1.1%) discontinued due to virologic failure, and 1 subject (1.1%) discontinued due to noncompliance with study drug.

Demographics and Baseline Characteristics

Overall, demographics and baseline disease characteristics were balanced across the treatment groups. Of the 267 subjects randomized and treated, 207 subjects (77.5%) had genotype 1 HCV infection, 12 subjects (4.5%) had genotype 2 HCV infection, 39 subjects (14.6%) had genotype 3 HCV infection, 8 subjects (3.0%) had genotype 4 HCV infection, and 1 subject (0.4%) in the SOF/VEL 24 Week group had genotype 6 HCV infection. The majority of subjects were male (69.7%), and 42.3% of subjects had a BMI ≥ 30 kg/m². Most subjects (55.1%) had prior treatment experience and the majority of subjects had HCV RNA $\geq 800,000$ IU/mL (55.8%).

Efficacy Results

The SVR12 rates were as follows:

- SOF/VEL 12 Week group: 83.3% (95% CI: 74.0% to 90.4%) of subjects (75 of 90) achieved SVR12

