1.4. Rationale for This Study

This Phase 2 study is designed as a multicenter, randomized, open-label study evaluating SOF/VEL FDC for 12 weeks and SOF/VEL + RBV for 12 weeks in subjects with Chronic GT3 HCV infection and compensated cirrhosis. Patients with genotype 3 HCV infection and cirrhosis have previously been studied as subgroups within 1 Phase 2 study (GS-US-342-0109) and 2 Phase 3 studies (GS-US-342-1140 [ASTRAL-3] and GS-US-342-1137 [ASTRAL-4]) evaluating either SOF + VEL or SOF/VEL FDC. GS-US-342-0109 is described in detail in the investigators brochure. Briefly, 27 and 26 patients with GT3 HCV infections without cirrhosis received SOF 400 mg + VEL 100 mg and SOF 400 mg + VEL 100mg + RBV, respectively, for 12 weeks, while 26 and 26 patients with compensated cirrhosis received SOF 400 mg + VEL 100mg and SOF 400 mg + VEL 100 mg + RBV, respectively, for 12 weeks. All patients without cirrhosis achieved SVR12, regardless of the addition of RBV, suggesting the RBV provides no additional efficacy when given to such patients. Among the patients with compensated cirrhosis, 88.5% achieved SVR12 without RBV while 96.2% achieved SVR12 with the addition of RBV, suggesting that RBV provides additional efficacy when added to regimens of SOF + VEL FDC in patients with GT3 HCV infections and cirrhosis. In ASTRAL-3 (described in Section 1.2.2.1.3), 277 patients with genotype 3 HCV were given SOF/VEL for 12 weeks, 80 (29%) of whom had underlying cirrhosis. The SVR12 rate for the cirrhotic patients was 91% compared to 97% for the non-cirrhotic patients. In ASTRAL-4 (described in Section 1.2.2.1.4) 14, 13, and 12 patients with genotype 3 HCV and decompensated cirrhosis (CPT B) received 12 weeks of SOF/VEL, 12 weeks of SOF/VEL + RBV, and 24 weeks of SOF/VEL, respectively. Of those patients, 7 (50%), 11 (85%), and 6 (50%) subjects achieved SVR12, suggesting that RBV provides additional efficacy on top of SOF/VEL when given to patients with GT3 HCV infections and decompensated cirrhosis.

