3. STUDY DESIGN

3.1. Treatment Plan and Regimen

This is a multicenter, randomized, open-label study that will evaluate the safety, tolerability and antiviral efficacy of SOF/VEL FDC with and without RBV for 12 weeks in subjects with chronic genotype 3 HCV infection and compensated cirrhosis with or without HIV co-infection.

Approximately 200 subjects with chronic genotype 3 HCV infection and compensated cirrhosis will be randomized (1:1) to either:

- Group 1 (n = 100): SOF/VEL once daily for 12 weeks

OR

- Group 2 (n = 100): SOF/VEL + RBV for 12 weeks

Randomization will be stratified by prior treatment experience (treatment naïve/treatment-experienced).

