3.4. Stopping Rules for Individual Subjects

Subjects who meet any of the following criteria should be discontinued from the study and complete an Early Termination Visit and return for Posttreatment Follow-up visits:

- Elevation of ALT and/or AST that is greater than the ULN and $> 5x$ baseline or nadir confirmed by immediate repeat testing unless laboratory results are assessed by both the investigator and Gilead Medical Monitor as having an explanation other than drug induced liver injury and it is deemed in the best interest of the subject to continue HCV treatment
- Confirmed elevation of ALT $>15 x$ ULN (unrelated to any interventional procedures)
- Confirmed total bilirubin $>10 x$ ULN (unrelated to any interventional procedures)
- Confirmed total bilirubin $>3x$ baseline or $3x$ nadir (unrelated to any interventional procedures)
- Any Grade 3 or greater rash associated with constitutional symptoms
- Any non-laboratory Grade 4 events assessed as related to administration of SOF/VEL
- Worsening of disease state as evidenced by progressing hepatic decompensation and/or progression of Child-Pugh Score (CPT) to ≥ 10

The Gilead Medical Monitor should be consulted prior to discontinuation of SOF/VEL and /or RBV unless the investigator believes that immediate action is warranted to ensure the continued safety of the subject.

Any questions regarding toxicity management should be directed to Gilead Medical Monitor.

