### 1.2. Study Design

This is a multicenter, randomized, open-label study that will evaluate the safety, tolerability, and antiviral efficacy of SOF/VEL FDC±RBV for 12 weeks in subjects with chronic genotype 3 HCV infection and compensated cirrhosis with or without human immunodeficiency virus (HIV) coinfection.

Approximately 200 subjects with chronic genotype 3 HCV infection and compensated cirrhosis will be randomized (1:1) to either:

- Group 1 (n = 100): SOF/VEL (400/100 mg) once daily for 12 weeks

OR

- Group 2 (n = 100): SOF/VEL (400/100 mg) once daily + RBV (1000 or 1200 mg divided into 2 daily doses) for 12 weeks

Randomization will be stratified by prior treatment experience (treatment naive or treatment experienced); treatment naive is defined as never having been exposed to an approved or experimental HCV-specific direct-acting antiviral (DAA) or having had prior treatment of HCV with interferon or RBV. All other subjects will be considered treatment experienced.

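### Inclusion 6 read literally lets cancer-exclusion imaging confirm cirrhosis, exclusion 2 leaves CPT 7 (class B) eligible in a trial called compensated, and no by-arm table shows CPT (minor)

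*Protocol*

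**What the plan says.** **Confirming cirrhosis.** Protocol 4.2, inclusion 6, is met by any one of four items: biopsy (6a), Fibroscan (6b), Fibrotest together with APRI (6c), or liver imaging within six months of Day 1 to exclude hepatocellular carcinoma (6d). Protocol 6.2.1 lists that imaging as a mandatory screening step. It also sends the site to Section 2 for the definition of cirrhosis status. SAP 5.2 recognises three determination methods: FibroTest with APRI, biopsy and elastography.

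**CPT limit.** Protocol 4.3, exclusion 2, removes "Child-Pugh-Turcotte (CPT) Score >7 at Screening". Exclusion 3 removes "Current, uncontrolled ascites, variceal hemorrhage, hepatic encephalopathy, hepatorenal syndrome, hepatopulmonary syndrome, or other signs of decompensated cirrhosis". Protocol Appendix 4 and SAP Appendix 3 both define class A as 5–6 points and class B as 7–9.

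**Population label.** Protocol 3.1 places the trial "in subjects with chronic genotype 3 HCV infection and compensated cirrhosis with or without HIV co-infection", and SAP 1.2 repeats "compensated cirrhosis with or without human immunodeficiency virus (HIV) coinfection". For ASTRAL-4, Protocol 1.2.2.1.4 says "Subjects with genotype 1 to 6 HCV infection with CPT class B cirrhosis were randomized (1:1:1"; Protocol 1.2.2.1 says "one study enrolled subjects with decompensated cirrhosis GS-US-342-1137 (ASTRAL-4"; and Protocol 1.4 refers to "patients with genotype 3 HCV and decompensated cirrhosis (CPT B".

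**Reporting.** SAP 5.2 summarises cirrhosis status by arm as yes, no or not determined. CPT score has an analysis window (SAP Table 3-1) and a by-subject listing (SAP 7.7, Listing 16.2.8.4), but no table.

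**The concern.** The primary result is one SVR12 proportion with an exact interval per arm, so the population description carries much of its meaning. Three things blur that description.

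First, imaging that excludes a tumour does not confirm cirrhosis, yet it sits in the list of sufficient confirmations. Second, the CPT cut-off admits a score that the appendices put in class B, a class the protocol calls decompensated when it describes another trial. Third, the planned baseline table uses an item that should hardly vary when cirrhosis is an entry condition, and omits the one that can. If score-7 subjects enrol, a reader of the tables could not see how many are in each arm.

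**Working it through.** **Inclusion 6.** Its logic is 6a or 6b or 6c or 6d. Protocol 6.2.1 requires the 6d imaging of every subject. Everyone who completes screening therefore satisfies 6d, and so inclusion 6, whatever the biopsy, Fibroscan or Fibrotest result. The 6.2.1 pointer does not rescue this, because Section 2 holds the objectives and defines nothing. Inclusion 6 is thus the only operative list of confirming methods. The three methods in SAP 5.2 match 6a–6c.

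**Is CPT 7 reachable?** Inputs are the five scored items in Protocol Appendix 4 (encephalopathy, ascites, bilirubin, albumin, PT or INR; 1–3 points each) and exclusions 3 and 5. I read the appendix's bilirubin as total bilirubin.

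- The minimum score is 5, so 7 needs two extra points: one item at 3 (5 ways) or two items at 2 (10 ways), 15 in all.
- No encephalopathy and no ascites (strict reading of exclusion 3): 3 + 3 = 6 ways remain.
- Albumin below 3 g/dL is excluded, so albumin cannot score 3 (below 2.8): 5 remain.
- INR held at 1 point: 2 remain, namely bilirubin 2 with albumin 2, and bilirubin 3 alone.

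Holding INR at 1 point is an assumption. Exclusion 5 allows INR up to 1.5 × ULN, and 2 points start at 1.7, so it needs ULN < 1.7/1.5 = 1.133. The documents do not give the ULN. At an assumed 1.1 the limit is 1.65 (1 point, 2 routes). At an assumed 1.2 it is 1.80, INR can score 2, and 4 routes remain. Under the hemophilia/anticoagulant waiver INR can score 3 and 5 remain. The counts also assume INR is scored. Protocol Appendix 4 allows PT instead, and exclusion 5 sets no PT limit.

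Worked example: encephalopathy none (1) + ascites none (1) + total bilirubin 2–3 mg/dL (2) + albumin 3.0–3.5 g/dL (2) + INR below 1.7 (1) = 7. Exclusion 5 limits direct bilirubin, not total, so this subject is eligible if direct bilirubin is within its limit and nothing else excludes.

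**Reporting.** SAP 7.2.1 summarises total bilirubin and INR by arm (Tables 15.11.6.1.3 and 15.11.6.1.11). Albumin is not on that list, and separate summaries of components cannot show how many subjects total 7.

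**Size.** With 100 per arm, k score-7 subjects, SVR12 of pA in the others and pB in these, the arm's rate lies below pA by

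pA − [(100 − k)pA + k·pB]/100 = k(pA − pB)/100, at most k percentage points.

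This ceiling holds for any subgroup of size k. The documents give neither k nor pB. The sample-size statement is untouched: the longest exact 95% interval at n = 100 is at 50/100, 39.83% to 60.17%, or 20.3 points, consistent with the stated 21%.

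**The case against.** Neither appendix labels class B decompensated; that equation appears only where the protocol describes other patients. For this trial, exclusion 3 defines compensation by clinical signs, and a subject who reaches 7 on laboratory values alone can fairly be called compensated. This stands, and it turns the CPT item from an error into a boundary the documents leave unreconciled. The on-treatment rule, "progression of Child-Pugh Score (CPT) to ≥ 10", is weak evidence either way, since it concerns worsening rather than entry.

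No CPT data are lost. The listing can be read against the listings of virologic failures and other outcomes, Protocol 9.4 permits further baseline items, and the bilirubin and INR tables give partial cover. This also stands; what is missing is a count by arm.

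On 6d, a reader might infer that subjects would really be enrolled on imaging alone. The documents do not support that. The synopsis and Section 6.2.1 keep cirrhosis assessment apart from tumour screening, SAP 5.2 omits imaging as a method, and the yes/no cirrhosis row would flag an ineligible subject. The item looks like a list slip, but the criterion as written still fails to do its job.

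**Conclusion.** The point holds and is minor. Inclusion 6 is wrong as worded. Exclusion 2, the class boundaries and the word compensated do not fit together. CPT is not summarised by arm. The number of score-7 subjects and any effect on SVR12 cannot be estimated from the documents. Both are probably small, since on the strictest reading only 2 of 15 routes to a score of 7 stay open.

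Three stronger readings are not supported:

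- *That SVR12 will be pulled down by a known amount.* The ASTRAL-4 genotype 3 rates (7 of 14 without ribavirin, 11 of 13 with it) come from class B as a whole, scores 7–9, in patients called decompensated. They do not estimate the response of score-7 subjects who pass exclusions 3 and 5.
- *That the arms are biased against each other.* No between-arm comparison is planned, and randomization balances case mix on average.
- *That CPT scores will differ between documents.* SAP Appendix 3 carries two scoring notes that Protocol Appendix 4 lacks, but the SAP does not say that site scores will be re-derived.

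**What to change.** - **Inclusion 6:** take 6d out of the list of sufficient confirmations, state it as the separate requirement already in Section 6.2.1, and point 6.2.1 to Section 4.2 instead of Section 2.
- **Population definition:** the sponsor should reconcile exclusion 2, the word compensated (Protocol 3.1, SAP 1.2) and the class boundaries in the appendices. A score of 7 may be intended, in which case the word needs a definition. No limit is proposed here.
- **Baseline table:** add screening CPT score and class by arm to SAP 5.2 and Table 15.8.3.2.
- **Editorial only:** use the same CPT scoring notes in both appendices.

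The cost is protocol wording and one baseline entry. CPT is already collected at screening and has an analysis window, so no new data are needed and the sample size does not change.
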